4 RESEARCH QUESTION/AIM(S)

4.1 Objectives

The purpose of this study is to explore the needs of people with painful HIV-SN for a psychologically-based treatment for managing chronic pain.

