walkingability, relations with others, sleep and enjoyment of life. The BPI has been shown to be a reliable and valid measure for use with people with neuropathic pain conditions, including peripheral neuropathy (39). Participants will also be asked to fill in a body map to indicate where they feel pain.

Neuropathic Pain Interview: The 7-item DN4-i (Douleur Neuropathique 4-interview, English version) interview (questionnaire version) will be conducted to identify the probability that the participant has neuropathic pain. A score of ≥ 3 out of 7 reflects a positive diagnosis of neuropathic pain (40) (41).

Patient Health Questionnaire (PHQ-9): The PHQ-9 (42) is a 10-item measure of the severity of depression symptoms based on the DSM-IV diagnostic criteria for depression. Each item is rated on a four point scale between 0 (not at all) and 3 (nearly every day). The PHQ-9 has shown reliability and validity as a measure of depressive symptoms and is commonly used as an outcome measure in studies of patients with chronic pain (42).

Interview Appointment

Assessment of neuropathy signs and symptoms

The Clinical HIV-associated Neuropathy Tool screening tool (12) will be administered at the beginning of the interview appointment (5 minutes). This 4-item tool comprises two subjective symptom questions (self-report of foot pain and foot numbness), and two objective signs on clinical examination (loss of vibration sense and loss of ankle reflex). Clinical examination of these signs does not require specialist medical training. Based on a previous study using the CHANT, patients are considered to have peripheral neuropathy if they are positive for one symptom and one sign in a bilateral distribution (43). Previous data indicate that the CHANT has 100% sensitivity and 85% specificity for diagnosing HIV-SN in a London-based sample in relation to a more comprehensive neurological examination (The Utah Early Neuropathy Score) as the reference standard (43). Information from the physical examination of the CHANT will be used to further support the case definition of peripheral neuropathy from the telephone screening. However, findings of positive signs from the physical examination are not a requirement for study inclusion and all participants will proceed to the semi-structured interview.

Semi-structured interview

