The interview schedule was developed on the basis of previous qualitative studies on psychological factors and treatments for pain in general and specifically in people with HIV (44, 45) and online CBT for pain management (46), and patient input. Participants will first be asked general questions about the impact of pain on their lives and how they currently cope with pain. They will also be asked more specific questions about their thoughts about an online psychological treatment for managing pain. While an interview schedule has been developed for the study, we expect questions to be further developed and revised during the study as data and themes emerge that require further probing.

[name] will conduct the interviews, which are expected to take approximately 1 hour each. Field notes will be made during/immediately after the interview to record the interviewer's impression of the participant's responses and the interview process. All interviews will be recorded using a dictaphone, transferred to a password-protected computer, and anonymised by [name]. [name] and a Bachelor's level (or higher) student or volunteer will transcribe the anonymized audio recordings verbatim.

Thematic analysis will be used to analyse the data following the recommendations of Braun and Clark (2006): Each transcript will be read in its entirety several times to establish familiarity. First level-descriptive codes will be annotated in the margin of the transcript. Second level codes will be used to summarize the most significant/frequent first-level codes; third-level codes will be used to identify higher order themes around which lower order themes are integrated. Quotes reflecting second-level themes will be extracted to demonstrate second-level themes for the final report (47). The NVivo 11.0 software program will be used to assist in data analysis. This process will be initially conducted by one coder; two additional coders will code 10% of the transcripts to establish the validity of the codes. Validity will also be established through use of the constant comparative method whereby the transcripts will repeatedly be reviewed to check that identified 2nd and 3rd level themes correspond to the data.

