7 SAMPLE AND RECRUITMENT

7.1 Eligibility Criteria

7.1.1 Inclusion criteria

- Adults aged 18 years or older.
- Living with HIV.
- A positive screen for peripheral sensory neuropathy, as indicated by: presence of self-reported bilateral foot pain and/or numbness in a symmetrical distribution (43).
- Positive screen for symptoms of neuropathic pain in the feet, as indicated by a score of >3 on the patient reported outcomes section of the Neuropathic Pain Interview, which has

previously been shown to have greater than 80% sensitivity and specificity for identifying people with neuropathic pain conditions (48, 49)

- Pain in the feet present most days for at least 3 months.
- Average pain intensity of ≥ 4 on a scale from 0 (no pain) to 10 (pain as bad as you can imagine)(50).
- Average interference of pain with daily activities is ≥ 4 on scale ranging from 0 (no interference) to 10 (unable to carry on any activities) (51).

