7.1.2 Exclusion criteria

- Presence of excessive alcohol consumption, hypothyroidism, vitamin B12 deficiency, diabetes, exposure to isoniazid or chemotherapy drug treatment, or a known history of a neuropathy due to a cause other than HIV or antiretroviral treatment (12, 52)
- Unable to conduct interview in English.
- Current diagnosis of dementia or learning disability.
- Unwilling to provide written informed consent.

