8.7 Data protection and patient confidentiality

All investigators will comply with the requirements of the Data Protection Act 1998 with regards to the collection, storage, processing and disclosure of personal information.

For patients recruited from Chelsea and Westminster Hospital (C&W), or participants recruited from the community who complete study procedures at C&W, participant identifying information will be stored on a secure NHS computer at C&W along with the anonymization log. Paper copies of consent forms will be stored in a locked filing cabinet in a locked room at C&W. All participants will be given an anonymous study identification number that will be used for screening, questionnaires, audio files and transcripts, so no identifiable information will be linked with these data. Anonymous questionnaire data will initially be collected on paper case report forms (CRF), which will be stored in a locked filing cabinet in a locked room at C&W. Data from paper CRFs will subsequently be entered in an electronic database stored on a secure computer.

Interviews will be recorded using a password protected dictaphone. The audio recording of interviews will be uploaded to a secure computer and any interview responses that identify the participant will be removed. Audio recordings will be erased from the dictaphone after being transferred to the computer. The anonymized audio files and questionnaire database will be transferred to a secure King's College London computer for analysis using an encrypted USB stick.

The identifying data of participants recruited from community organizations who complete study procedures at King's College London will be stored on a secure King's College London (KCL) computer at Guy's Hospital. Hard copies of consent forms will be stored in a locked filing cabinet in a secure room at KCL. Paper copies of anonymized questionnaires will likewise be stored in a locked filing cabinet in a secure room at KCL. The anonymized electronic questionnaire database, audio files and transcripts will be stored on a secure KCL computer. All audio files will be destroyed after they have been transcribed.

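### Does the thematic analysis need a step that uses the CHANT examination before its themes are reported as the needs of people with painful HIV-SN?

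*Combined protocol and SAP*

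**What the plan says.** The objective in Section 4.1 is to "explore the needs of people with painful HIV-SN for a psychologically-based treatment for managing chronic pain". Entry under Section 7.1.1 rests on self-report: bilateral, symmetrical foot symptoms, a positive neuropathic pain screen, foot pain on most days for at least 3 months, and average intensity and interference of 4 or more. Section 7.1.2 excludes several listed alternative causes and "a known history of a neuropathy due to a cause other than HIV or antiretroviral treatment".

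The CHANT is described in Section 5 under the assessment of neuropathy signs and symptoms. It has two symptom questions and two examined signs. A rule from a previous study is cited: neuropathy is taken as present with one symptom and one sign, bilaterally. Sensitivity of 100% and specificity of 85% are quoted. The stated use is that "Information from the physical examination of the CHANT will be used to further support the case definition of peripheral neuropathy from the telephone screening". The text then adds that "findings of positive signs from the physical examination are not a requirement for study inclusion and all participants will proceed to the semi-structured interview".

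The analysis paragraph, also in Section 5, sets out three levels of coding, a check of 10% of transcripts by two additional coders, and constant comparison, in which "the transcripts will repeatedly be reviewed to check that identified 2nd and 3rd level themes correspond to the data". It does not refer to the CHANT.

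**The concern.** The plan collects an objective measure on everyone, gives it a purpose, and then shows no step that carries the purpose out. The objective, the tailoring of the treatment (Section 4.2) and the sampling statement (Section 7.2.2, Sampling technique) all name people with painful HIV-SN. Everyone enrolled already reports foot symptoms, so CHANT status turns on the signs. With the quoted sensitivity of 100%, a CHANT-negative participant would not have HIV-SN by the cited reference standard.

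If several such participants were interviewed, a reader could not tell how many there were, or whether a theme came only from them. At stake would be the labelling and transferability of themes that feed a later feasibility trial. No estimate or test is affected, because the study has none.

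**Working it through.** **Plan's own figure.** The sample of about 30 (Section 7.2.1) rests on convention and saturation. It has no formula, so there is nothing to reproduce.

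**Reading the text.** Three points in the protocol, set side by side:

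- Section 5 names the telephone screen as the case definition, gives the examination a supporting role, and discloses that signs are not needed. Section 7.1.1 agrees. There is no contradiction.
- The analysis paragraph covers transcripts only. It is equally silent on the Brief Pain Inventory, body map, DN4-i, PHQ-9 and demographic items. The omission is general to a short qualitative plan and not particular to the CHANT.
- Nothing in it prevents the sample from being described by these measures.

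**How many CHANT-negative participants?** The documents do not give the share of enrolled participants with HIV-SN, so it must be assumed.

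Inputs: N = 30 (Section 7.2.1); CHANT sensitivity 1.00 and specificity 0.85 (Section 5). A screen of 80%/80% is borrowed from Section 7.1.1, where a figure of over 80% refers to neuropathic pain and not to neuropathy. Priors of 90% and 70% are assumed for targeted recruitment. A prior of 40% is the low end of the range for all people with HIV (Sections 1 and 2). A screen specificity of 50% is assumed.

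Formulas:

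- PPV = prior × sens / [prior × sens + (1 − prior) × (1 − spec)]
- Non-cases = 30 × (1 − PPV)
- CHANT-negative, upper = 0.85 × non-cases
- CHANT-negative, lower = non-cases × [1 − 0.15 / (1 − screen spec)]. This applies if every non-case who would be CHANT-positive also passes the symptom screen.

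| Prior, screen | PPV | Non-cases | CHANT-negative |
|---|---|---|---|
| 90%, 80/80 | 0.72/0.74 = 0.973 | 0.81 | 0.20 to 0.69 |
| 70%, 80/80 | 0.56/0.62 = 0.903 | 2.90 | 0.73 to 2.47 |
| 40%, 80/50 | 0.32/0.62 = 0.516 | 14.52 | 10.16 to 12.34 |

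A second route starts from an assumed share π with HIV-SN among those enrolled. The expected number of CHANT-negatives is 30 × (1 − π) × 0.85, and P(at least one) = 1 − [1 − 0.85(1 − π)]^30.

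| π | Expected CHANT-negative | P(at least one) |
|---|---|---|
| 95% | 1.28 | 73% |
| 90% | 2.55 | 93% |
| 80% | 5.10 | 99.6% |
| 70% | 7.65 | >99.9% |

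If the CHANT's specificity among symptomatic people were 50% (assumed), π = 90% would give 30 × 0.10 × 0.50 = 1.5.

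**Reading the numbers.** At least one CHANT-negative participant is likely. Under targeted recruitment the number is small. The figures of 10 to 12 apply a general HIV prevalence to a sample found through consultants, a previous painful-neuropathy cohort, adverts and chain referral (Section 7.3.1).

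**The case for a change.** The best case for a change is that the examination is the only objective neuropathy information the study collects, and its stated purpose is not carried into analysis or reporting. Second-level codes summarise the first-level codes that matter most or occur most often, so who is pooled could affect which themes advance. The remedy would be cheap: an NVivo attribute, a count, and a comparison during a transcript review already planned. Section 8.7 gives a common identifier: "All participants will be given an anonymous study identification number that will be used for screening, questionnaires, audio files and transcripts". That list does not name the examination form, so the link is inferred, though it is a natural one.

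What stands is that the text is silent and that the count of CHANT-positive and CHANT-negative participants is worth reporting. The rest carries less weight:

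- The inference that a CHANT-negative participant lacks HIV-SN depends on a point estimate given without sample size or interval, from a reference listed as submitted.
- Specificity of 85% may not hold where everyone has symptoms.
- A one-sided sign makes a participant CHANT-negative without being sign-negative.
- The interviews ask about the impact of pain, coping and online treatment. All participants share the same pain entry criteria, and the documents give no reason for answers to vary with ankle reflex or vibration sense.
- A theme held by only one or two people would seldom reach the higher coding levels, and chance could explain it if it did.

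**Conclusion.** No change to the plan is needed. The protocol adopts a symptom-based case definition, says so, and keeps participants without signs deliberately. No stated rule, number or analysis is wrong. What is missing is reporting detail that analysts following Section 5 would supply in the sample description: the number CHANT-positive and CHANT-negative by the cited rule, with a note on the source of the accuracy figures. A check of themes by CHANT status would suppress no theme and alter only a label. It is optional, and informative only if more than a few participants are CHANT-negative.

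The size is uncertain: about 0.2 to 2.5 of 30 with priors of 70% to 90% and an 80%/80% screen, and 5.1 to 7.65 if only 80% to 70% of those enrolled have HIV-SN. All of these rest on assumed shares and on the quoted CHANT accuracy. The conclusion does not depend on which holds, because entry, interviews and the themes reported would be the same in each case.

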4.2 Outcome

The interview responses will be used to develop and tailor an internet-delivered version of ACT for people with painful HIV-SN. Once developed, the new treatment will be tested in a feasibility trial (another study). It is hoped that tailoring the online ACT treatment based on the qualitative interview responses will increase the acceptability of the treatment and will improve treatment adherence rates.

5 STUDY DESIGN and METHODS of DATA COLLECTION AND DATA ANALYSIS

Participants will complete semi-structured interviews. Prior to the in-depth interview, participants will complete a questionnaire package at home to bring to their interview appointment (20-30 minutes to complete). The questionnaire package will consist of demographic and medical history questions, and symptom and functioning questionnaires. Individual in-depth semi-structured interviews will be conducted given the potentially sensitive nature of the questions and to maintain participants' anonymity. Participants will be given the choice to complete the interviews at the Imperial College London campus of Chelsea & Westminster Hospital or Guy's Hospital Campus of King's College London, according to their preference.

At the beginning of the interview appointment, the interviewer will conduct a 5 minute clinical examination to assess of symptoms and signs related to peripheral neuropathy. In the event that questionnaires are not completed prior to the interview session, participants will be asked to complete the questions at the interview appointment or at home and to mail them back in within 2 weeks. Participants who have not completed the questionnaires 3 weeks after the interview will receive a telephone reminder.

Pre-Interview Questionnaires

Demographic, Medical History, and Internet Use Questions: Participants will be asked to report on the following demographic and medical history questions: age, gender, ethnicity, sexual orientation, education, employment status, living situation, date of HIV diagnosis, history of and current antiretroviral treatment, duration of foot pain, other chronic pain diagnoses, mental health diagnoses, current pain medications, current alcohol and drug use, and frequency of Internet use.

Pain intensity and interference: The Brief Pain Inventory (BPI) will be used to assess pain intensity and the interference of pain with daily functioning in seven domains: general activity, mood,

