7.2 Sampling

7.2.1 Size of sample

Approximately 30 participants will be recruited, with roughly equal representation of men, women, ethnic minorities, and people who use recreational drugs. Recruitment will terminate once saturation of themes has been achieved. Thus, while an approximate sample size has been estimated on the basis of convention in qualitative methods and the range of demographic characteristics being sought (53, 54), an exact sample size cannot be determined a priori.

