7.2.2 Sampling technique

Men and women, ethnic minorities, and people who use recreational drugs will be purposively sampled through HIV and pain clinics and community organizations and through chain referral sampling. Purposive sampling across participants with the range of demographic backgrounds identified will ensure that the interview responses are reflective of people with painful HIV-SN who might ultimately be referred to and receive the psychologically-based pain management treatment being developed.

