8.4 Patient & Public Involvement

[name] and [name] are patient representatives located at St. Stephen's Centre at Chelsea and Westminster Hospital and at King's College Hospital, respectively. [name] were consulted about the study during the application for funding of a fellowship to undertake a larger project to develop and test the feasibility of an online psychologically-based pain management treatment for people with painful HIV-SN. Both [name] were enthusiastic about the potential benefits of the new treatment, but identified patient engagement as an important issue. This input solidified the need to incorporate a qualitative study of barriers to patient engagement for the proposed online treatment, which will feed into further treatment development.

The patient representatives were involved in the design of the research in several ways. [name] suggested that a multi-pronged recruitment strategy was the most appropriate to ensure we capture the views of the diversity of people with painful HIV-SN. This informed our recruitment strategy. [name] did not feel that peer/patient interviewers for the qualitative study were appropriate, and, therefore, it was decided that a researcher ([name]) would conduct the interviews. [name] also suggested suitable remuneration (e.g., vouchers) for participants in the interview study. [name] reviewed study documents (e.g., recruitment adverts, information sheet, consent form, questionnaires, and interview schedule) and made several suggestions for re-wording, which were incorporated into the current version of the documents. UKCAB, which is an advocacy group of people living with HIV, also provided feedback on the study documents, which was also incorporated.

[name] will be consulted to provide input on the themes coded from the transcribed interviews to ensure their relevance and appropriateness. [name] will also review a study report that will be given to patients following completion for the study to ensure its comprehensibility and sensitivity.

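### Is second coding of 10% of the transcripts too small and too loosely specified to support the validity of the codes?

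*Combined protocol and SAP*

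**What the plan says.** Section 5 (Semi-structured interview) sets out a three-level thematic analysis. It starts with descriptive coding: "First level-descriptive codes will be annotated in the margin of the transcript". Second-level codes then summarise the most important or most frequent of these, and third-level codes draw them into higher-order themes. On who does the work, the protocol says "This process will be initially conducted by one coder" and then "two additional coders will code 10% of the transcripts to establish the validity of the codes".

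The sentence after that names constant comparison as a further basis for validity, in which "the transcripts will repeatedly be reviewed to check that identified 2nd and 3rd level themes correspond to the data". Section 8.4 adds a consultation: patient and public input is planned in which named contributors "will be consulted to provide input on the themes coded from the transcribed interviews to ensure their relevance and appropriateness".

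On the sample, Section 7.2.1 states: "Approximately 30 participants will be recruited, with roughly equal representation of men, women, ethnic minorities, and people who use recreational drugs". The number is approximate because recruitment stops at saturation. The section on sampling technique confirms that "Men and women, ethnic minorities, and people who use recreational drugs will be purposively sampled". On use of the results, Section 4.2 says "The interview responses will be used to develop and tailor an internet-delivered version of ACT for people with painful HIV-SN", with testing left to a separate feasibility trial.

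**The concern.** Three transcripts is a small base for a step described as establishing validity. Nothing requires those transcripts to include each sampled group, although the sample was made diverse so that the treatment would reflect all of them. Nothing says that the additional coding must come before the codes are settled, when it could still alter them.

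The other two checks do not plainly fill the gap. Constant comparison is described as testing second- and third-level themes, and the consultation concerns themes already coded. Neither is described as independent coding. For first-level codes, the 10% step is the only direct check described.

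If the second-coded transcripts happened to omit one group, what that group said about its needs would be coded by one person only, and that coding would feed into the tailored treatment.

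**Working it through.** **Inputs.** About 30 interviews (Section 7.2.1), 10% second-coded and two additional coders (Section 5). The protocol does not give the method of selection, the group sizes or how common any code is. Random selection, groups of 15 and the code frequencies below are therefore assumptions.

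**Number of transcripts.** 0.10 × 30 = 3 if both coders take the same ones; 2 × 3 = 6 if each takes a different 10%. If saturation gave 20 to 40 interviews (assumed range), the counts would be 2 to 4, or 4 to 8.

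**Chance that a code is never met.** For a code present in K of 30 transcripts, with n drawn at random, P(miss) = C(30−K, n) / C(30, n). For example, K = 6 and n = 3 gives C(24,3)/C(30,3) = 2024/4060 = 0.50.

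| Code present in | n = 3 | n = 6 |
|---|---|---|
| 3 of 30 | 0.72 | 0.50 |
| 6 of 30 | 0.50 | 0.23 |
| 9 of 30 | 0.33 | 0.09 |
| 15 of 30 | 0.11 | 0.01 |

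**Chance that a group is left out.** Assume 15 men, 15 women, 15 participants from ethnic minorities and 15 who use recreational drugs, and write q = C(15, n)/C(30, n). If minority membership and drug use are independent of each other and of gender, P(at least one group missed) = 1 − (1 − 2q)(1 − q)².

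- n = 3: q = 455/4060 = 0.112, giving 1 − 0.776 × 0.788 = 0.39.
- n = 6: q = 5005/593775 = 0.0084, giving 0.03.
- Over every possible overlap of four groups of 15, the range is 0.22 to 0.40 for n = 3 and 0.02 to 0.03 for n = 6.

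**What deliberate choice would do.** Taking every participant as a man or a woman, one transcript from an ethnic-minority participant, one from a participant who uses recreational drugs, and a third of whichever gender is still missing will cover all four groups. The chance of leaving out a group is then 0 with only 3 transcripts.

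Deliberate choice helps less with uncommon codes. For a code held by 6 people, all in one group of 15, with j of the 3 transcripts from that group, P(miss) = C(9, j)/C(15, j): 1.00 for j = 0, 0.60 for j = 1 and 0.34 for j = 2.

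**What a larger share would do.** At 20% (6 transcripts coded by both), a code in 3 of 30 would still be missed half the time under random choice.

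**Timing.** The timeline (Table 1) runs data analysis from November 2016 to August 2017, and interviews from November 2016 to July 2017. Section 5 expects questions to be revised as themes emerge, and Section 7.2.1 stops recruitment at saturation. Coding therefore has to proceed while interviews continue, which leaves room for second coding before the codes settle, though no sentence guarantees it.

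**The case for a change.** The best case for a change is that it costs almost nothing. One sentence could say that the 10% will span the sampled groups and be coded independently before the codes are final. It would need no new staff or participants, and only the amendment route in Section 8.9. First-level codes decide what can become a theme, and the protocol's own background says that these groups' perspectives are not usually built into such treatments. A check that may skip one of them fits poorly with that rationale.

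Part of this stands. The details are absent, the arithmetic is right, and a code that is rare but important would have only limited independent scrutiny.

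The rest does not carry a change:

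- The same silence permits deliberate choice (group risk 0) or six different transcripts (2% to 3%). The 22% to 40% figure needs random choice, identical transcripts and groups of 15 all at once.
- Having both coders read the same 3 transcripts gains two independent readings but loses reach if different ones were intended (0.50 against 0.23 for a code in 6 interviews). That is a trade-off, and neither side is clearly better.
- Earlier second coding changes nothing by itself unless disagreements are resolved in some stated way.
- Saying that the step supports validity, in place of establishing it, alters wording only.
- First-level codes that matter are carried into second-level themes, which are repeatedly checked against the transcripts. That check is indirect and not independent, but it is a check.

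**Conclusion.** No change to the plan is needed. The protocol leaves out how the 10% is chosen, whether the coders share transcripts, when they code and how differences are settled. These are working details of an iterative qualitative analysis, and a sensible team can decide them within the present text. No stated rule produces a wrong result, and nothing in the documents shows 10% to be too small.

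Validity is presented as resting on second coding and constant comparison together, with consultation on the themes in addition, so the word *establish* should not be tested against the 10% step alone. The miss probabilities (0.50 or 0.23 for a code in 6 of 30 interviews; 22% to 40% or 2% to 3% for a group left out) describe the reach of one check under assumed random selection and, for the group figures, assumed group sizes of 15. A code that the additional coders do not meet is not thereby invalid. What remains is modest and confined mainly to uncommon first-level codes, and the tailored treatment goes on to a separate feasibility trial.
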